### **5.5 Subject Compliance Monitoring**

Study team will assess and track subject compliance with the study treatment regimen by asking patient about compliance with daily dosing. Patients will be reminded weekly to take daily dosing at the same time each morning. Patients will be required to bring back their pill bottles at each visit. There will be a pill count at each visit conducted by the study coordinator. Patients who are significantly non-compliant will have their safety assessed by study doctor and withdrawn from the study.

### **5.6 Prior and Concomitant Therapy**

Any medication or non-pharmacological therapy that is taken by or administered to the subject at any point during the course of the study must be recorded in the case report form (CRF).

#### **Prior Medications Allowed/Disallowed During Study**

Subjects taking stimulant or non-stimulant medications for the treatment of ADHD during screening will be washed out for a period equivalent to 5 half-lives of the medication prior to baseline evaluations.

#### **Disallowed Medications during Study**

CONFIDENTIAL

Use of any of the following medications is not permitted during the study;

- 1) Antidepressant prescription medication (e.g., paroxetine, sertraline, venlafaxine, monoamine oxidase [MAO] blocker, tricyclic, etc.) and St. John's Wort.
- 2) Anticonvulsant medications (e.g., phenytoin, carbamazepine, lamotrigine, valproic acid, etc.) and antipsychotic medication.
- 3) Sedating antihistamines (e.g., doxilamine succinate, diphenhydramine) for use in sedation or aiding with sleep. Subjects routinely use sedating antihistamines for seasonal allergies will be required to switch to non-sedating alternatives for the duration of the study, unless otherwise contraindicated.
- 4) Other medications that may interfere with the assessment of cognitive function are not permitted during the study.

### **5.7 Packaging (Pharmacy)**

- Study drug and placebo is supplied in 20mg, 30mg, 40mg, 50mg, 60mg, and 70mg capsules in bottles containing #9 pills each. The bottles will be labeled with Patient's name, study identification number, Study name and NYU IRB number, study drug name, study drug dosage, strength, quantity, directions for usage and physician's name and contact information.
- Study drug will be shipped in bulk # 40 bottles at each shipment.

### **5.8 Blinding of Study Drug**

The study drug is double blinded. The research staff; including study doctor and the patient will not know if the patient is receiving Vyvanse or placebo. The study pharmacist will know which study medication either Vyvanse or Placebo the patient is taking and can break the blind in case of an emergency.

### **5.9 Receiving, Storage, Dispensing and Return**

#### **5.9.1 Receipt of Drug Supplies**

Shire pharmaceuticals will ship the study drug quantity for sufficient for patients to be enrolled and treated at NYULMC via the NYU Investigational Drug Service (IDS), contact number [contact]. Upon receipt of the of the study treatment supplies, an inventory must be performed and a drug receipt log filled out and signed by the person accepting the shipment. It is important that the designated

CONFIDENTIAL

study staff counts and verifies that the shipment contains all the items noted in the shipment inventory. Any damaged or unusable study drug in a given shipment (active drug or comparator) will be documented in the study files. The investigator must notify study sponsor of any damaged or unusable study treatments that were supplied to the investigator's site.

### **5.9.2 Storage**

Study medication will be dispensed in a tight, light-resistant container as defined in the USP. The study medication will be stored at 25° C (77° F). Excursions permitted to 15-30° C (59-86° F)

### **5.9.3 Dispensing of Study Drug**

The study doctor will write a prescription for the patient noting that the study drug name is listed as Vyvanse/Placebo. The research coordinator will call pharmacist to prepare the study medication. Study coordinator will fax the prescription to the pharmacist, who will randomize the patient and give the patient a randomization number. The paper prescription will be taken to the investigational pharmacy by study coordinator to be filled and dispensed by research pharmacist, directly to the patient. An electronic record of the order will also be entered into the EPIC system by the research physician and verified by the investigational pharmacist. The study drug will be prepared, labeled and dispensed by the research pharmacist from the NYU Investigational Drug Service (IDS), contact number [contact]. Used study bottles/pills will be returned to the investigational pharmacist at each dispensing visit. Dispensing/ Return logs will be used and documentation of pills dispensed and pills returned will be documented weekly.

### **5.9.4 Return or Destruction of Study Drug**

At the completion of the study, there will be a final reconciliation of drug shipped, drug consumed, and drug remaining. This reconciliation will be logged on the drug reconciliation form, signed and dated. Any discrepancies noted will be investigated, resolved, and documented prior to return or destruction of unused study drug. Drug destroyed on site will be documented in the study files.

## **6 Study Procedures:**

CONFIDENTIAL

This material is the property of the NYU School of Medicine and Langone Medical Center. Do not disclose or use except as authorized in writing by the study sponsor

	Visit 1	Visit 2	Visit 3	Visit 4	Visit 5	Visit 6	Visit 7	Visit 8	Visit9	Visit 10	Visit 11
Study Procedures and Assessments	Week -3-0	Week 0	Week 1	Week 2	Week 3	Week 4	Week 6	Week 7	Week 8	Week 9	Week 10
	Screening	Baseline 1	Treatment (LDX or PBO) 1			EOT 1	End of PBO Washout/ Baseline2	Treatment (LDX or PBO) 2			EOT 2
SCREENING											
Consent	X										
Demographics	X										
M.I.N.I	X										
ACDS v1.2	X										
Medical History	X										
Psychiatric History	X										
Medical Review of Systems	X										
Physical Exam	X										
Hematology, Chemistry, Urinalysis, and UDS	X										
Urine Pregnancy Test	X										
ECG	X										
Review Eligibility	X	X	X								
EFFICACY											
ADHD-RS		X		X	X	X	X	X	X	X	X
Barkley SCT Scale		X		X	X	X	X	X	X	X	X
CGI-S		x		X	X	X	X	X	X	X	X
SAFETY											
Vital Signs		X	X	X	X	X	X	X	X	X	X
C-SSRS		X	X				X	X			X
Concomitant Medications		X	X	X	X	X	X	X	X	X	X
Adverse Events		X	X	X	X	X	X	X	X	X	X
NEUROPSYCHOLOGICAL BATTERY/EXECUTIVE FUNCTIONING											
CANTAB ADHD		x					X	X			X
WAIS-CODING & SYMBOL SEARCH		X					X	X			X
BRIEF-A		X					X	X			X
BFIS		X					X	X			X
ON-TOP		X									
OTHER											
Dose Dispense/ Adjustment			X	X	X	X			X	X	X
Drug Accountability				X	X	X	X	X	X	X	X

CONFIDENTIAL

This material is the property of the NYU School of Medicine and Langone Medical Center. Do not disclose or use except as authorized in writing by the study sponsor

**STUDY VISIT SCHEDULE:** This is a two part study. Patients will sign this consent form and be asked to do the following: Visit the study doctor weekly over a 12-week period, communicate over the phone between visits 6 and 7 and approximately 1 week after visit 10, and follow study instructions. In addition, patients who participate in the second part of the study will be asked to take study drug as instructed at the same time each day. Patient will have their blood drawn once in the study about 10mls will be collected for hematology and blood chemistry.

### **6.1 Visit 1 (Screening) Week -3 to Week 0**

Screening (Visit 1) (Phenotype Phase): Informed consent, demographics, medical/psychiatric history, physical exam, review of systems, 12-lead electrocardiogram (ECG), vital signs, ADHD diagnosis via ACDS v1.2, M.I.N.I (assessment of other Axis-I psychiatric diagnosis), laboratory testing (hematology, blood chemistry and urinalysis), urine pregnancy screen (for female participants), urine toxicology screen, Clinical Global Impressions Scale (CGI) [22], C-SSRS, Neuropsychological Battery, and prior and concomitant medications (CM))

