## 4.2 Exclusion Criteria

- 1) Meets DSM-IV-TR criteria for a primary diagnosis of hyperactive-impulsive type ADHD as diagnosed via the ACDS v1.2.
- 2) Any other current psychiatric disorder, determined via the M.I.N.I , which requires pharmacotherapy treatment.
- 3) Current suicidal ideation or history of suicide attempts, based on the Columbia-Suicide Severity Rating Scale(C-SSRS) [15].
- 4) Lifetime history of bipolar disorder or any psychotic disorder as per the M.I.N.I
- 5) Pregnant, breastfeeding or women planning to become pregnant.
- 6) Positive urine drug toxicology are excluded.
- 7) Any other reason that, in the opinion of the investigator, prevents the subject from participating in the study or compromise the subject safety.

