### **5.2 Treatment Regimen**

Medication will not be dispensed until week 1 of the study. Then for four weeks the dose of LDX or Placebo will be dispensed starting at 30mg up to 70 mg per day with an intervening single-blind placebo washout period (2 weeks).

Block One: During the LDX/epoch, LDX/Placebo treatment will be initiated at a dose of 30mg/day at Visit 2 and can be titrated up (in the judgment of the investigator) in

CONFIDENTIAL

increments of 20mg, based upon clinical response and tolerability, to 50mg/day at Visit 3 and 70mg/day at Visit 4.

Subjects receiving daily doses of 50mg or 70mg of LDX/Placebo will be allowed to down titrate one dosage step of 20mg during Visits 3-5 if (in the judgment of the investigator) they are having issues in tolerability. The highest effective dose of LDX will then be maintained until Visit 6.

Placebo Washout: At this time the patient are in the washout placebo phase for two weeks.

Block Two: At the end of the Placebo Washout Phase, Visit 7 (week 6), participants will be initiated at a dose of 30mg/day and can be titrated up starting at Visit 8 (in the judgment of the investigator) in increments of 20mg, based upon clinical response and tolerability.

Subjects receiving daily doses of 50mg or 70mg of LDX/Placebo will be allowed to down titrate one dosage step of 20mg during Visits 8-10 if (in the judgment of the investigator) they are having issues in tolerability. The highest effective dose of LDX will then be maintained until Visit 11

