**6.6 Visit 7 (Baseline 2) Day 42±2; Week 6**

Visit 7 will consist of ADHD-RS with prompts, Barkley SCT Scale, BRIEF-A, Barkley Functional Impairment Scale (BFIS), neuropsychological battery, CGI, vital signs, assessment of adverse events (AE) and concomitant medications (CM). Study Medication is dispensed. Drug accountability is performed.

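### The only scheduled pregnancy test is at Visit 1, so placebo-first women start LDX at Visit 7 with a test that is 42 to 63 days old

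*Combined protocol and SAP*

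**What the plan says.** Section 4.2, item 5, excludes "Pregnant, breastfeeding or women planning to become pregnant". Section 8.5 discontinues a participant who becomes pregnant. Section 1.2 says the drug is not for use in pregnancy, and allows use only where the expected benefit justifies the fetal risk.

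The test that supports the exclusion appears once. Section 6.1 lists a "urine pregnancy screen (for female participants" at screening. In the schedule table of section 6, the row "Urine Pregnancy Test" is marked under Visit 1 only. The row "Review Eligibility" is marked at Visits 1, 2 and 3 and not again.

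The second block starts at "Visit 7 (Baseline 2) Day 42±2; Week 6". Section 5.2 says: "At the end of the Placebo Washout Phase, Visit 7 (week 6), participants will be initiated at a dose of 30mg/day". Section 6.6 says: "Visit 7 will consist of ADHD-RS with prompts, Barkley SCT Scale, BRIEF-A, Barkley Functional Impairment Scale (BFIS), neuropsychological battery, CGI, vital signs", followed by adverse events and concomitant medications, and then: "Study Medication is dispensed. Drug accountability is performed". It names no pregnancy test and no eligibility review.

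**The concern.** The plan checks pregnancy with an objective test before a woman enters treatment. For women randomised to LDX first, that test is recent when the drug is given, and Visit 2 adds a review of history and eligibility. For women randomised to placebo first, the same drug is given for the first time six weeks later on the strength of the same test. Only the randomised order separates the two groups.

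At stake is avoidable fetal exposure. If the schedule is followed as written, a placebo-first woman with an unrecognised pregnancy that began after Visit 1 is given LDX at Visit 7. The benefit-risk judgement in section 1.2 cannot be made for a pregnancy nobody knows about.

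The evidence in section 1.2 is mixed. Animal studies of this drug showed no effect on embryofetal morphology or survival. Animal studies of amphetamine showed lasting neurochemical and behavioural effects, and premature delivery and low birth weight were seen in infants of amphetamine-dependent mothers.

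**Working it through.** **Inputs**

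- Visit 1, when the test is done: Week -3 to Week 0, so Day -21 to Day 0 (6.1 and schedule table).
- Visit 2, first dispensing: Day 0 (6.2).
- Visit 7, start of Block 2: Week 6, Day 42±2 (6.6).
- Expected numbers: 50 enter treatment and 44 complete washout (3.1).
- Assumption: 1:1 allocation to order. Section 5.3 specifies block randomisation but gives no ratio.

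**The plan's own timing.** 6 weeks × 7 = Day 42, which agrees with the day stated for Visit 7.

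**Age of the only test when LDX is dispensed** (dispensing day minus test day)

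| Order | Shortest | Longest |
|---|---|---|
| LDX first (Visit 2) | 0 - 0 = 0 days | 0 - (-21) = 21 days |
| Placebo first (Visit 7, nominal) | 42 - 0 = 42 days | 42 - (-21) = 63 days |
| Placebo first (Visit 7, ±2 days) | 40 - 0 = 40 days | 44 - (-21) = 65 days |

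If the first capsule is taken the next morning, as 6.2 says for Visit 2, the nominal placebo-first range becomes 43 to 64 days. Section 6.2 lets unfinished screening assessments be completed at Visit 2. That could put the test at Day 0, which is the lower bound already used; it is not a second test.

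**Size of the group.** Placebo-first patients at Visit 7: 44 / 2 = 22. With 25 starting in each order and 50 - 44 = 6 lost before Visit 7, the range is 25 - 6 = 19 to 25 - 0 = 25. These counts include both sexes. The documents do not give the number of women able to become pregnant, so no count of conceptions can be derived.

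**What a Visit 7 test would change.** Let L be the number of days after conception before a urine test turns positive. The documents do not give L.

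- Now: no test can show a conception in the last (42 to 63) + L days before Visit 7.
- With a test at Visit 7: only conceptions in the last L days are missed.
- Difference: 42 to 63 days, whatever L is.

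The same reasoning at Visit 2 gives a reduction of 0 to 21 days.

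**The case against.** The best case for the plan is that these weeks are not unmonitored. Women planning a pregnancy are excluded at entry. Visits 3 to 6, the week 5 call (6.5) and Visit 7 itself are all contacts at which 8.2 requires specific adverse event questioning, with examination as appropriate. Section 8.5 acts once a pregnancy is known. A pregnancy several weeks old has therefore had several chances to be reported, and the 42 to 63 days gained is time not covered by a test, not time without any safeguard. That stands, and it limits the expected number of exposures. It does not close the gap. Excluding women who plan a pregnancy does not detect an unplanned one, and questioning finds what is known or symptomatic. Symptoms are also a weak signal here, because section 1.6.1 lists nausea and vomiting as drug effects and blinded staff could attribute them to study medication.

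Other points on that side are partly right:

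- No passage promises a repeat test, and the laboratory tests, ECG and drug screen are also done at screening only. This is a design choice, not a broken rule.
- The eligibility row sits under the screening heading, so its absence at Visit 7 is not a separate defect. It matters only because it means no other listed step would prompt a pregnancy check.
- LDX-first women can conceive during Block 1, and a Visit 7 test would find that only after exposure. This is true, and the proposed test does not address it.
- Section 3.1 also mentions 80 patients entering treatment, so the head-count is uncertain. The interval does not depend on it.
- The dispensing row of the table shows no mark at Visit 7. Sections 5.2 and 6.6 are explicit that drug starts and is dispensed there.
- The attachments and consent pages were not available and may contain pregnancy instructions. If they require a Visit 7 test, the table and 6.6 should still show it.

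**Conclusion.** The concern holds. As scheduled, placebo-first women receive their first LDX 42 to 63 days after their only pregnancy test (40 to 65 with the visit window), against 0 to 21 days for LDX-first women. On the plan's retention figures and an assumed 1:1 order, about 22 patients of both sexes (19 to 25) are placebo-first at that point; the women able to become pregnant are an unknown part of them.

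The timing rests on the schedule table and section 6 alone. The frequency of the event cannot be estimated from the documents and is likely to be low. The consequence is a possible avoidable fetal exposure. Power, type I error and the treatment estimate are not affected. Visit 2 is a lesser matter: the test is at most 21 days old there, and history and eligibility are reviewed before drug is given.

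**What to change.** Add the urine pregnancy test already used at Visit 1 to Visit 7, before dispensing, for women able to become pregnant. Do it in both orders, because staff are blinded to order (5.8). Mark it in the schedule table and in section 6.6, and state that a positive result leads to discontinuation under 8.5. A repeat at Visit 2, when Visit 1 was not on or close to Day 0, is optional.

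The cost is one urine dip test per eligible woman at an existing visit with existing staff, plus a short amendment. The ceiling is 44 tests at Visit 7, reached only if everyone who completes washout is a woman able to become pregnant, and at most 50 more if Visit 2 is added. Conceptions in the last L days, and those within a block, would still depend on questioning, examination as appropriate and the discontinuation rule.

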### **6.2 Visit 2 (Baseline 1) Day 0**

Baseline visit: During this visit subjects will have all tests/procedures completed and reviewed. We will review medical history, any current of adverse events (AE) and concomitant medications (CM) since screening visit. We will perform vital signs and C-SSRS. We will ensure completion of any assessments not finished during the screening visit. Subjects will be given medication to take the next morning if they are found to have both ADHD and SCT. Study Medication is not dispensed until all assessments and procedure are complete for the baseline visit

Note: If at the end of this baseline visit, the patient is found to have both ADHD and SCT; they will be invited to continue to the second part of the study. If the patient has both ADHD and SCT, he/she will be given Study Medication (Vyvanse or placebo) to take the next morning. Placebo looks just like Vyvanse but has no active ingredients, like a sugar pill. The study medication can be taken with or without food at the same time every day.

CONFIDENTIAL

**6.3 Visits 3, 4, & 5 (Treatment) Day 7±2, Day 14 ±2, and Day 21±2; Weeks 1-3**

Visits 3, 4, and 5 will occur at 7, 14, and 21 days (±2 days) from Baseline. These visits will consist of ADHD-RS with prompts, Barkley SCT Scale, CGI, vital signs, and assessment of adverse events (AE) and concomitant medications (CM). Study Medication is dispensed.

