**6.7 Visits 8, 9, & 10 (Treatment) Day 49±2, Day 56±2, and Day 63±2; Weeks 7-9**

Visits 8 through 10 will consist of the ADHD-RS with prompts, Barkley SCT Scale, CGI, vital signs, assessment of adverse events (AE) and concomitant medications (CM). Study Medication is dispensed. Drug accountability is performed.

CONFIDENTIAL

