## 7.2 Statistical Methods

Phenotype Phase: Comparisons between the adult ADHD patients cohorts with SCT and without SCT in terms of ADHD symptoms (total, inattentive and hyperactive-impulsive, symptoms of executive function (BRIEF GEC, metacognition, behavioral regulation scales and subscales: Inhibit, Shift, Emotional Control, Initiate, Working Memory, Plan/Organize, Organization of Materials, Monitor), neuropsychological tests (CANTAB ADHD module, WAIS Coding and Symbol Search and Attention Network Test (ANT), and impairment (on Barkley Functional Impairment Scale (BFIS)) will be examine via One Way ANOVA .

Treatment Phase: Changes in outcome ratings in the patients in the treatment phase with LDX and placebo will be modeled with longitudinal generalized estimating equation (GEE) mixed regression models using STATA 12.0 [StataCorp, 2011 #25856] within the framework of the general linear model (GLM). The GLM allows us flexibility in modeling the outcome variable by choosing the appropriate distribution and link function. Each model will predict outcome scores from treatment group (drug vs. placebo), study visit (ordinal predictor), order (drug or placebo first) and the two and three-way interactions among: treatment group, visit, and order. We will first test for order effects and drop effects that are not significant at  $p < .05$ . The visit by treatment interaction indicates if the reduction in symptoms over time significantly differs between drug and placebo. Our primary analyses will be intention

CONFIDENTIAL

[SHIRE SCT s13-01288]  
Version: 03/03/2016

to treat (ITT) but we will explore the data with less conservative per protocol analyses to assure that we do not miss any signals in the data. Because this is a randomized trial, which follows subjects over a short period of time, missing data is not expected to impact our analyses. Should this become an issue, we will impute data using STATA's impute procedure. Using logistic regression, a responder analysis will be conducted using pre-hoc priori criteria for treatment response (30% decreases in total ADHD-RS and Barkley SCT scores). These will be last observation carried forward (LOCF) endpoint models that predict responder status (yes/no) from drug group, order and the drug by order interaction. Baseline symptom scores will be included as covariates.

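### The schedule table leaves the three efficacy ratings blank at Visit 3 although section 6.3 requires them; if sites follow the table, week 1 is rated in block 2 only

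*Combined protocol and SAP*

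**What the plan says.** Section 6.3 fixes the timing, "Visits 3, 4, and 5 will occur at 7, 14, and 21 days (±2 days) from Baseline", and the content, "These visits will consist of ADHD-RS with prompts, Barkley SCT Scale, CGI, vital signs". Section 6.7 does the same for block 2: "Visits 8 through 10 will consist of the ADHD-RS with prompts, Barkley SCT Scale, CGI, vital signs".

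The schedule table in section 6 has eleven visit columns. Its Barkley row reads "Barkley SCT Scale X X X X X X X X X": nine marks, at Visit 2 and Visits 4 to 11. The ADHD-RS and CGI-S rows have the same pattern. By contrast, "Vital Signs X X X X X X X X X X" has ten marks, at Visits 2 to 11. C-SSRS, concomitant medications and adverse events are also marked at Visit 3, so the Visit 3 column is present and only the efficacy cells in it are empty. Visit 8 carries all three ratings in both table and text.

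Section 7.2 models the outcome on treatment, "study visit (ordinal predictor), order (drug or placebo first) and the two and three-way interactions among: treatment group, visit, and order". It takes the visit-by-treatment interaction as the evidence that symptoms fall faster on drug than on placebo.

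**The concern.** The Barkley SCT Scale and the ADHD-RS are the two primary measures named in section 2, and the protocol gives two instructions for when they are first rated on treatment. A site working from the table would skip the week-1 rating in block 1 and take it in block 2. Two sites with their own staff could also resolve the conflict differently.

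In a two-sequence crossover the loss is not neutral. Each patient contributes to both treatments at a given week only if that week is rated in both blocks. If week 1 is rated in block 2 alone, a patient's week-1 treatment is fixed by the sequence. The week-1 comparison is then between patients and coincides with order, and the interaction that section 7.2 interprets rests on less information. Ratings not taken cannot be recovered later.

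**Working it through.** **Inputs.**
- Rating schedule: section 6 table, 6.3 and 6.7.
- Model terms: 7.2.
- Two sequences by block randomization: 5.3. The ratio is not stated; 1:1 is assumed.
- n = 45 evaluable, effect size 0.6, two-sided 0.05, stated power 80%: 3.1.
- Within-patient correlation ρ: not given. Compound symmetry with ρ = 0.3, 0.5 or 0.7 and outcome SD 1 are assumed.

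**Step 1. The plan's own figure.** For 45 pairs with ρ = 0, the noncentrality is 0.6/√2 × √45 = 2.85, and paired-t power is 79.5%. For 45 per arm in parallel it is 80.4%. Either reproduces the stated 80%. The figure concerns the change from baseline to week 4, so Visit 3 does not enter it.

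**Step 2. Week-1 cells.**

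| Sequence and treatment | Visit | Rated under 6.3 / 6.7 | Rated under the table |
|---|---|---|---|
| LDX first, on LDX | 3 | yes | no |
| Placebo first, on placebo | 3 | yes | no |
| LDX first, on placebo | 8 | yes | yes |
| Placebo first, on LDX | 8 | yes | yes |

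**Step 3. Visit categorical, order terms kept.** The model has 4 weeks × 2 treatments × 2 orders = 16 parameters. Under the text there are 16 cells and rank 16. Under the table there are 14 cells and rank 14. At week 1 alone, the intercept, treatment, order and treatment-by-order terms (4 parameters) face 2 cells, so the rank is 2. At week 4 all four cells remain, and the standard error ratio is 1.00.

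**Step 4. Visit as a linear score, order terms kept.** Each sequence-by-treatment cell has its own slope, with variance (1−ρ)σ²/((n/2)·S), where S is the sum of squared deviations of the rated weeks.
- Weeks 1 to 4: S = 5. Weeks 2 to 4: S = 2.
- The treatment-by-visit slope compares one block-1 slope with one block-2 slope. Its variance is proportional to 1/5 + 1/5 = 0.40 with Visit 3 rated, and to 1/2 + 1/5 = 0.70 without.
- Ratio 0.70/0.40 = 1.75; √1.75 = 1.32. The standard error rises 32%, whatever ρ is.
- With baselines as week-0 outcomes, S = 10 with Visit 3 and 8.75 without. (1/8.75 + 1/10)/(2/10) = 1.071; √1.071 = 1.035, a rise of about 3.5%.

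**Step 5. Visit as a linear score, order terms dropped.** Generalized least squares with n = 45:

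| ρ | Slope SE, Visit 3 rated | Slope SE, Visit 3 not rated | Ratio |
|---|---|---|---|
| 0.3 | 0.0789 | 0.0936 | 1.19 |
| 0.5 | 0.0667 | 0.0794 | 1.19 |
| 0.7 | 0.0516 | 0.0616 | 1.19 |

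With baselines modelled as outcomes, the rise is about 3%.

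**Step 6. The week-1 contrast alone.** Between patients its variance is 4σ²/n; within patients it is 2(1−ρ)σ²/n. The ratio 2/(1−ρ) is 2.9, 4.0 or 6.7, so the standard error is 1.7, 2.0 or 2.6 times larger. If order terms are dropped and the model borrows from other visits, the factor is about 1.5 (0.264/0.176, 0.225/0.149, 0.176/0.115). That is valid only without an order or period effect at week 1.

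**Step 7. Endpoint analyses.** Under the table, a block-1 patient who attends Visit 3 and leaves before Visit 4 has no post-baseline rating to carry forward into the LOCF responder models of 7.2. Under 6.3 that patient has one.

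**The case against.** The best defence is that section 6.3 is explicit and nothing shows that the sponsor meant to skip the rating. The table disagrees with section 6 elsewhere too. BRIEF-A, BFIS and the neuropsychological tests are marked at Visits 7 and 8 but described at Visits 6 and 7 (6.4, 6.6). Dispensing is marked at Visits 3 to 6 and 9 to 11, while 6.2, 6.6 and 6.7 also describe it at Visits 2, 7 and 8. The blank is therefore plausibly clerical. This stands, and it makes the harm conditional on sites following the table. It does not remove the conflict, because the table is also an instruction to sites.

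Several stronger readings are tempting, and the documents do not support them:
- **That the primary comparison is compromised.** Section 3.1 powers the trial on week 4, and Step 3 shows no change there. No week-1 endpoint is defined.
- **That the model cannot be fitted.** Section 7.2 calls visit an ordinal predictor without saying how it is coded, and drops non-significant order effects. Rank is lost only with categorical visits and order terms kept.
- **That standard errors grow 1.7 to 2.6 times.** This describes a raw single-visit contrast, not the interaction that 7.2 interprets.
- **That the first dose decision lacks its evidence.** Section 5.2 says "based upon clinical response and tolerability, to 50mg/day at Visit 3" and refers to the investigator's judgment. No passage ties it to a scale score.
- **That many patients lose their endpoint.** Section 3.1 expects 50 − 46 = 4 losses over the whole first phase. It also restricts analysis to patients dosed in both blocks, which would exclude these patients anyway, although 7.2 says intention to treat.

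**Conclusion.** The contradiction is certain: three efficacy rows are blank at a visit where section 6.3 requires all three ratings, and nothing says which governs. The statistical cost arises only if the table is followed. In that case up to 50 ratings per scale are lost, one of four on-treatment ratings per patient in block 1. Treatment and order are then inseparable at week 1 if visit is categorical and order terms are kept. If visit is a linear score, the interaction stays estimable with a standard error about 19% to 32% larger, or about 3% larger if baselines are modelled as outcomes. Section 7.2 does not settle which of these models applies. The slope figures assume compound symmetry and 1:1 sequences; the 32% figure does not depend on the correlation, and the 19% figure hardly does. The week-4 comparison is untouched. This is a moderate defect, worth correcting because the lost ratings cannot be replaced.

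**What to change.** Mark ADHD-RS, Barkley SCT Scale and CGI-S at Visit 3 in the schedule table, so that it agrees with 6.3 and mirrors Visit 8. In the same revision, check every row of the table against section 6. The BRIEF-A, BFIS and neuropsychological rows (Visits 7 and 8 against Visits 6 and 7) and the dispensing row need to be reconciled with the text. It would also help to state which of table and text governs if they differ. The cost is table edits and a few minutes of rating at a visit patients already attend; the sample size, the visits and the analysis do not change.
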